Moulin, 1997 ²²	1776	Increased 30 day mortality, RR 1.007 (1.004, 1.010)		
Williams, 2002 ³	634	Increased 30 day mortality if glucose \geq 130 mg/dL, HR 1.87 (1.05,3.32), p=0.018		
Gentile et al, 2006 ²	960	Increased mortality if glucose \geq 130mg/dL, p<0.004		
Reduced favorable clinical Weir, 1997 ²³		at 3 months with admission hyperglycemia		
,	645	p<0.001. Only patient w/o diabetes analyzed		
TOAST, Bruno, 1999 ²⁴	1259	p=0.03. All study patients (Rx and placebo)		
Demchuk, 2001 ²⁵	616	p= 0.03. All patients treated with tPA		
ATLANTIS, Bruno, 2002 ²⁶	755	p<0.001. All study patients, (tPA and placebo)		
NINDS tPA, Bruno, 2002 ²⁶	624	p=0.02. All study patients (tPA and placebo)		
CASES, Poppe, 2009 ²⁷	1098	RR=0.7 (0.5,0.9) if glucose >144mg/dL (tPA patients)		
Worse clinical outcomes wi	ith in-hos	pital hyperglycemia		
Gentile et al, 2006 ²	960	Increased mortality if glucose ≥130 mg/dL, p<0.001		
ECAS-II, Yong, 2008 ²⁸	587	Reduced favorable outcome if glucose >140 mg/dL, OR=0.36 (0.13,0.71)		
Fuentes, 2009 ²⁹	476	Increased poor outcome if glucose ≥155 mg/dL, p=0.002		
Dziedzic, 2009 ³⁰	689	Increased 90 day mortality, HR 1.10 (1.03,1.18), p<0.01		
TOAST = Trial of ORG 10172 in Acute Stroke Treatment; ATLANTIS = the acute stroke rt-PA 3-5 hours after onset of symptoms treatment trial:				

ATLANTIS = the acute stroke rt-PA 3-5 hours after onset of symptoms treatment trial;

NINDS rt-PA = the NINDS rt-PA Acute Stroke Trial;

CASES = Canadian Alteplase Stroke Effectiveness Study

Of importance is the finding that glucose concentrations after admission are also associated with worse clinical outcomes. These data suggest that clinical outcomes may be impacted by normalization of blood glucose in the first few days after stroke.

Table 2. Association between acute hyperglycemia and infarct volume on MRI					
1 st author, yr	Number of	Definition of	Outcome associate		
	Subjects	hyperglycemia	with hyperglycemia		
Parsons, M	40	>144 mg/dL	Larger infarcts, less		
2002^{31}			penumbral salvage, higher		
			brain lactate		
Els T, 2002 ³²	31	>178 mg/dL	Greater lesion expansion		
Baird TA, 2003 ³³	20	>126 mg/dL	Greater lesion expansion		
Ribo M, 2007 ³⁴	47	>140 mg/dL	Greater lesion expansion		

In summary, the majority of data from observational studies show an independent association between both admission and in-hospital (first several days) hyperglycemia with worse clinical and imaging outcomes in acute ischemic stroke patients.

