8.2.2 Blinding Set Up

- The SHINE trial is single blinded to the subject throughout the study (the treating team will be unblinded to treatment) and then is double blinded to include the examiner for the 90 day efficacy outcome assessment.
- Patients in both groups will receive an IV treatment (insulin or saline) and subcutaneous treatment (insulin or saline).

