8.7 Schedule of Events

Table 5. Abbreviated Schedule of events in SHINE trial						
Event	Screen*	Baseline*	Up to 3 days of Rx	Complete Rx/ D/C**	6 wks	90 days
Informed Consent	X					
Eligibility Assessment	X					
Randomization		X				
Study drug given		x				
Finger stick glucose check	X	x				
mRS ⁵⁵ , BI ¹³					X	X
NIHSS ¹²		X	x (daily)	X		X
SSQOL ¹⁴						X
SAE/AEs*		x				X
Protocol Deviations		x				X
Neuro worsening		x				
Lacunar subtype				X		

^{*}Screening is during eligibility assessment; baseline is at time of randomization. AEs will be followed through the treatment period only. SAEs will be reported throughout the study.

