12.2.3 Primary Efficacy Analysis

The primary outcome analysis of the 90-day mRS will use a stratified dichotomy methodology for assessing improvement as defined in the Primary Outcome section above. Outcome differences will be analyzed under the intention-to-treat principle, therefore all randomized subjects will be included in the primary analysis sample. To assess efficacy, the treatment groups will be compared with respect to the proportion with favorable outcome 90 days post randomization after controlling for the prognostic variables included in the randomization scheme. A Wald chi-square test will be performed to compare the treatment group proportions using a two-tailed significance level of 0.05. Adjusted relative risks will be reported with two-sided 95% confidence intervals.

Additional analyses will identify potential confounding (prognostic) variables to be used as covariates in subsequent secondary analyses of the primary outcome using generalized linear modeling techniques. Specific covariates include age, gender, race, ethnicity, admission blood glucose, previous stroke, time between stroke onset and treatment and lacunar subtype. If statistically significant differences are evident, post-hoc analyses will be conducted to determine if differences had an effect on the conclusions from the pre-specified primary analysis.

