10.1.2 Primary Efficacy Analysis at the End of the Trial

The primary outcome analysis of the 90-day mRS will use a stratified dichotomy methodology for assessing improvement as defined in the Primary Outcome section above. Outcome differences will be analyzed under the intention-to-treat principle, therefore all randomized subjects will be included in the primary analysis sample. To assess efficacy, the treatment groups will be compared with respect to the proportion with favorable outcome 90 days post randomization after controlling for the variables included in the randomization scheme. The primary statistical analysis will develop a generalized linear model using the PROC GENMOD procedure in SAS® v9 with treatment group as the factor of interest and baseline NIHSS strata (3-7, 8-14, 15-22) and thrombolysis use (Yes/No; includes both IV and IA therapies) as covariates. A Wald

[figure not shown]
chi-square test will be performed to compare the treatment group proportions using a two-tailed significance level of 0.05. Adjusted relative risks will be reported with two-sided 95% confidence intervals. Additional analyses will identify potential confounding (prognostic) variables to be used as covariates in subsequent secondary analyses of the primary outcome. Specific covariates include age, gender, race, ethnicity, admission blood glucose, previous stroke, lacunar subtype, and time between stroke onset and treatment. If statistically significant differences are evident, then post-hoc analyses will be conducted to determine if differences had an effect on the conclusions from the pre-specified primary analysis.

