10.2 Secondary Outcome Variable Analysis

This study is designed to test the primary hypothesis. However, it also offers the opportunity to conduct analyses to evaluate important additional neurological and functional outcomes using the NIHSS, BI and SSQOL. All secondary analyses will be conducted using the intention to treat study population. Favorable outcomes for the NIHSS and BI are defined as: a score of 0 or 1 on the NIHSS and a score of 95-100 on the BI at 90 days post randomization. Because there are only three secondary efficacy outcomes, adjustment for multiplicity will not be made. Each of these dichotomous outcomes will be analyzed using a chi-square test at a significance level of 0.05. With a study sample size of 1400, we have 80% power to detect absolute differences in favorable outcome for the: NIHSS of 7% (assuming control group is 25%) and BI of 8% (assuming control group is 40%). The SSQOL 90-day score will be analyzed as a continuous outcome. Mean scores overall and for each domain will be compared between the two treatment arms, adjusting the alpha level for multiple testing. Secondary analyses of all secondary outcomes will adjust for the specific covariates that are listed above in the primary analysis section as well as additional covariates identified at the time of analysis.

In addition to the above clinical outcomes, we also will examine/compare blood glucose measurements over time as well as protocol conduct metrics between treatment arms: time to target, time in target, early/late time to treatment and adherence to the computerized glucose monitoring system.

Secondary Outcome	Definition	Descriptive Statistics
Time to Target	(Randomization Time – Time Target is met (hrs)); target met defined as BG of 70-180 in the control arm and BG of 70-130 in the treatment arm.	Two-sided 95% confidential intervals; means, Comparison of means between treatment arms.
Time in Target	Blood Glucose Measurements During Treatment	Proportion of measurements out of target; area under the curve; box plots over time (every 4hrs) by treatment arm and by primary outcome.
Time to Treatment	Randomization Time - Stroke Onset Time (hrs)	Comparison of means between treatment arms.
Time on Treatment	Randomization Time – Infusion stop time (Form 15)	Comparison of means between treatment arms.

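### Lacunar subtype is scheduled only at end of treatment or discharge, yet it is a covariate in the secondary adjusted analyses; take it from pre-randomisation information or drop it there

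*SAP*

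**What the plan says.** **The models.** The primary model in SAP 10.1.2 contains "treatment group as the factor of interest and baseline NIHSS strata (3-7, 8-14, 15-22) and thrombolysis use", and nothing else. The same section then adds a supportive layer: "Additional analyses will identify potential confounding (prognostic) variables to be used as covariates in subsequent secondary analyses of the primary outcome". The variables are named: "Specific covariates include age, gender, race, ethnicity, admission blood glucose, previous stroke, lacunar subtype, and time between stroke onset and treatment". Protocol 12.2.3 has the same list in a different order: "Specific covariates include age, gender, race, ethnicity, admission blood glucose, previous stroke, time between stroke onset and treatment and lacunar subtype". Both sections close with a conditional step: if significant differences are found, post-hoc work will examine whether they bear on the primary conclusion.

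SAP 10.2 carries the list further: "Secondary analyses of all secondary outcomes will adjust for the specific covariates that are listed above in the primary analysis section". The main tests of the NIHSS and Barthel Index outcomes are chi-square tests without covariates.

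**The timing.** In Table 5 (protocol 8.7) the row "Lacunar subtype" has one mark, in the column for completion of treatment or discharge. The screening and baseline cells are empty. The footnotes place baseline at randomisation, and the later visit at the end of the 72-hour course or at discharge if that comes first.

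**The blinding.** Protocol 8.2.2 states that "the treating team will be unblinded to treatment". SAP section 7 agrees: the subject and the 90-day assessor are blind, the site treatment team is not.

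Neither document defines lacunar subtype, says who assigns it, or says which images are used.

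**The concern.** A covariate-adjusted treatment comparison is safe when the covariates could not have been influenced by the assigned arm. Lacunar subtype stands beside age and previous stroke as if it met that condition, but it is scheduled after study treatment has been given.

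The documents suggest two ways in which the arm could reach the label:

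- **Biology.** The trial's rationale is that hyperglycaemia enlarges infarcts. Table 2 in protocol 3.2 summarises three of its four imaging studies as "Greater lesion expansion". If glucose control limits expansion, the infarct seen at 72 hours, and so its classification, could differ by arm.
- **Knowledge of the arm.** If a member of the unblinded team assigns the label, borderline cases could be classified differently in the two arms.

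The adjusted analyses serve to show whether the primary result is robust. A label moved by treatment could make a real effect look partly explained by stroke type, and a drift in labelling could produce an adjusted difference where there is no effect.

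**Working it through.** No figure in the plan depends on this variable, so there is none to reproduce. The check has two parts.

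**1. Is lacunar subtype the odd one out?**

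- The Table 5 columns can be cross-checked. The mRS and Barthel marks fall at 6 weeks and 90 days, which fits the follow-up in protocol 8.4 and the use of a 6-week mRS in SAP section 8. The daily NIHSS marks fit protocol 8.1.4. The single lacunar mark therefore belongs at end of treatment or discharge.
- Age, gender, race, ethnicity, admission glucose and previous stroke are known before randomisation. Time from onset to treatment is fixed by the start of treatment; the SAP 10.2 table even computes time to treatment from the randomisation time.
- Lacunar subtype is thus the only named covariate scheduled after treatment has been given.

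**2. How far could an adjusted estimate move?**

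Inputs from the documents: favourable rates of 25% and 32% (SAP 4.1) and 1400 subjects, taken as 700 per arm.

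Assumed, because the documents give no values: 20% labelled lacunar in the control arm, with favourable rates of 45% in lacunar and 20% in other strokes. These reproduce the control rate: 0.20 × 0.45 + 0.80 × 0.20 = 0.25. The outcome gap is 45 − 20 = 25 points.

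Let *s* be the excess share labelled lacunar in the IV arm, with the same gap in both arms. The adjusted difference *d* solves

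(0.20 + *s*) × 0.45 + (0.80 − *s*) × 0.20 + *d* = IV-arm rate,

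so *d* = crude difference − *s* × gap.

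| Label shift *s* (points) | *s* × gap (points) | *d* if crude difference is 7 | *d* if crude difference is 0 |
|---|---|---|---|
| 0 | 0 | 7.0 | 0 |
| 1 | 0.25 | 6.75 | −0.25 |
| 5 | 1.25 | 5.75 | −1.25 |
| 10 | 2.5 | 4.5 | −2.5 |

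A shift in the other direction reverses the sign and inflates the adjusted effect.

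*Scale.* The standard error of the crude difference is √[(0.25 × 0.75 + 0.32 × 0.68)/700] = √(0.4051/700) ≈ 0.024, or 2.4 points. The three non-zero shifts are worth about 0.1, 0.5 and 1 standard error. As a fraction of 7 points they are about 4%, 18% and 36%.

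*Wider assumptions.* A Mantel-Haenszel calculation was run over lacunar shares of 15–35% and outcome gaps of 10–30 points. Under no effect, relabelled patients were given either the non-lacunar or the lacunar outcome rate.

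- No true effect: a 5-point shift gives −0.4 to −1.6 points, and shifts of 3 to 10 points give −0.3 to −3.3.
- True effect of 7 points: a 5-point shift gives 5.5 to 6.5 points, and shifts of 3 to 10 points give 4.0 to 6.7.
- No shift: no bias in any case.

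**The case against.** Much of the opposing case stands.

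- **Scope.** A reader might infer that the trial's main analysis conditions on a post-randomisation label. It does not. The primary model is adjusted, but only for NIHSS stratum and thrombolysis use. Its alpha, power and interim boundaries are untouched, as are the chi-square tests of the NIHSS and Barthel outcomes.
- **Use of the result.** A reader might infer that these adjusted models can overturn the primary conclusion. The text provides only a conditional, post-hoc examination, and nothing lets it replace the prespecified result.
- **Nature of the variable.** Subtype describes the index stroke, which precedes randomisation. Late recording does not make it a consequence of treatment. Table 5 is an abbreviated schedule, the Manual of Procedures is not available here, and imaging is required for eligibility, so a label based on pre-treatment images is not excluded. That the rater is unblinded is likely but not stated.
- **Mechanism.** The Table 2 studies, of 20 to 47 subjects each, concern infarct size and lesion growth. None is described as showing a change in lacunar classification.
- **Size.** Apart from 25% and 32%, every input to the calculation is assumed. A 5- or 10-point shift from 20% means 25% or 50% more lacunar labels in one arm, and the documents give no support for that.

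What does not fall away is the plan as written. It prespecifies adjustment for a label scheduled after up to 72 hours of open treatment, with no source or rater stated. Inspecting the data at the end will not repair this: an imbalance in the discharge label could be chance, where adjustment helps, or an effect of the arm, where it misleads. The table of labels by arm cannot tell these apart.

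**Conclusion.** The point holds for the secondary covariate-adjusted analyses of the primary outcome and, through SAP 10.2, for the secondary analyses of the secondary outcomes. It does not reach the primary analysis.

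Any bias depends on treatment or knowledge of the arm changing the label. That is plausible from the protocol's own rationale and its blinding arrangements, but it is not demonstrated, and the stronger claim that these analyses are biased is not supported. If the label does shift, the bias is about the shift times the outcome gap: 0.25, 1.25 and 2.5 percentage points for shifts of 1, 5 and 10 points at an assumed gap of 25.

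At the smaller shifts this is minor. At the larger ones it is a noticeable part of the 7-point difference that the plan treats as the threshold for a worthwhile therapy. It should be corrected, as a modest defect in supportive analyses.

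**What to change.** In protocol 12.2.3 and SAP 10.1.2, state that lacunar subtype is used for adjustment only if it is derived from clinical and imaging information obtained before randomisation, preferably by a rater blind to arm. If that cannot be done, drop it from the main secondary adjusted models. SAP 10.2 follows automatically, because it refers back to the same list.

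Tabulate the discharge label by arm. If a model using that label is kept, present it as a sensitivity analysis, with and without the covariate, and do not use it to qualify the primary conclusion. A total ban on the covariate would go further than the evidence supports.

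The cost is a few words in each document. The primary analysis, sample size and alpha do not change. The small downside is that a label from pre-randomisation information is likely to be less accurate than one assigned at discharge, and so will explain slightly less variance.

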10.1.3 Interim Analysis Plan

The study is designed using four interim looks for both efficacy and futility of the primary outcome and one final look for a total of 5 planned analyses of the primary outcome. The interim analysis plan uses the error spending function method with O'Brien and Fleming (OBF) type stopping guidelines⁷⁻⁹. The error spending function distributes the type I and II error rates across the interim monitoring points giving the flexibility of changing the intervals of monitoring while still preserving the overall type I and II error rates. The OBF-type boundary is considered conservative as its boundaries make it difficult to terminate a study early on by requiring extreme early evidence of efficacy or futility. It spends smaller amounts of alpha at the first look and gradually increases the spending as more information is acquired. The trial may be stopped for overwhelming efficacy of one treatment group over the other or for futility at the planned interim analyses if the test statistic crosses the respective boundaries.

The current plan is to conduct the first interim analysis after approximately 500 randomized subjects complete the primary outcome assessment (90-day mRS). Assuming an accrual rate of 33.3 patients per month, it is anticipated that the 1st look will occur roughly 2.5yrs from the start of enrollment. Subsequent analyses will occur after every additional 200 subjects complete the 90-day mRS (i.e., 700, 900, and 1100). The interval may be altered if requested by the DSMB. The stopping boundaries are defined using the gamma family spending functions with a gamma value of -4 (closely resembles OBF boundaries)¹⁰. Specific to the futility boundaries, they are derived as non-binding meaning that if a futility boundary is crossed there is the ability for it to be overruled without inflation of the type 1 error rate. If the crossing of an efficacy boundary is overruled, then this decision can impact the type II error rate but not the type I error rate. EAST[®] 5 software (Cytel Corporation) was used for the boundary calculations.

The below graph depicts the stopping boundaries based on the test statistic at each planned look. The inner wedge represents rejection of the alternative (futility) and the outer boundaries represent rejection of the null (overwhelming efficacy). The boundaries have the property that under the null hypothesis of no difference the overall probability of crossing either outer boundary does not exceed the overall type I error rate and under the alternative hypothesis the overall probability of crossing the inner boundary does not exceed the type II error rate. Appendix A provides further details on the properties of the stopping boundaries.

The following table lists the test statistics (shown in the above graph) and the corresponding p value as well as the probability of crossing either of the boundaries (futility or efficacy) at a particular look. Using the 5th column as an example, under the null hypothesis of no difference, the probability of crossing the specified boundary for either efficacy or futility is 0.05 at the 1st look, 0.10 for the 2nd look and so forth. Overall the probability of stopping the study (for futility) by the 4th look is 0.75 under the null and 0.66 under the alternative (stopping for efficacy).

Analysis	Approximate Sample Size	Minimum Test Statistic Z value (p value) to reject H ₀	Minimum Test Statistic Z value (p value) to reject H _a	Boundary Crossing Probabilities Under H ₀	Boundary Crossing Probabilities Under H ₁
1	500	2.97 (0.003)	0.06 (0.949)	0.05	0.12
2	700	2.86 (0.004)	0.13 (0.896)	0.10	0.13
3	900	2.65 (0.008)	0.45 (0.652)	0.27	0.19
4	1100	2.42 (0.016)	1.05 (0.293)	0.33	0.22
Final	1400	2.02 (0.043)	2.02 (0.043)	0.25	0.34

The SDMC will be responsible for conducting these analyses and compiling the reports for the DSMB. Since several factors need to be taken into consideration before stopping a study, safety and study progress also will be taken into consideration by the DSMB

and Executive Committee in the decision to stop the study if an efficacy or futility boundary is crossed.

10.2 Secondary Outcome Variable Analysis

This study is designed to test the primary hypothesis. However, it also offers the opportunity to conduct analyses to evaluate important additional neurological and functional outcomes using the NIHSS, BI and SSQOL. All secondary analyses will be conducted using the intention to treat study population. Favorable outcomes for the NIHSS and BI are defined as: a score of 0 or 1 on the NIHSS and a score of 95-100 on the BI at 90 days post randomization. Because there are only three secondary efficacy outcomes, adjustment for multiplicity will not be made. Each of these dichotomous outcomes will be analyzed using a chi-square test at a significance level of 0.05. With a study sample size of 1400, we have 80% power to detect absolute differences in favorable outcome for the: NIHSS of 7% (assuming control group is 25%) and BI of 8% (assuming control group is 40%). The SSQOL 90-day score will be analyzed as a continuous outcome. Mean scores overall and for each domain will be compared between the two treatment arms, adjusting the alpha level for multiple testing. Secondary analyses of all secondary outcomes will adjust for the specific covariates that are listed above in the primary analysis section as well as additional covariates identified at the time of analysis.

In addition to the above clinical outcomes, we also will examine/compare blood glucose measurements over time as well as protocol conduct metrics between treatment arms: time to target, time in target, early/late time to treatment and adherence to the computerized glucose monitoring system.

Secondary Outcome	Definition	Descriptive Statistics
Time to Target	(Randomization Time – Time Target is met (hrs)); target met defined as BG of 70-180 in the control arm and BG of 70-130 in the treatment arm.	Two-sided 95% confidential intervals; means, Comparison of means between treatment arms.
Time in Target	Blood Glucose Measurements During Treatment	Proportion of measurements out of target; area under the curve; box plots over time (every 4hrs) by treatment arm and by primary outcome.
Time to Treatment	Randomization Time - Stroke Onset Time (hrs)	Comparison of means between treatment arms.
Time on Treatment	Randomization Time – Infusion stop time (Form 15)	Comparison of means between treatment arms.

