12. STATISTICAL CONSIDERATIONS

12.1 Sample Size and Power Estimation

The primary outcome variable is the overall proportion of subjects experiencing a favorable outcome 90-days post randomization, where favorable is defined by the dichotomized mRS score as adjusted to the baseline NIHSS (stroke severity). Our preliminary data suggest a 25% rate of favorable outcome in the control group at 90 days is reasonable. A clinically relevant absolute difference in success rates between the two interventions is chosen as 7% (see preliminary data) (success rate_{control}=25%; success rate_{infusion}=32%). If the IV insulin group does not have at least a 7% or higher success rate than the control group, then IV insulin within 12 hours of symptom onset will not be considered a worthwhile therapy for hyperglycemic acute ischemic stroke subjects.

Based on the above information and taking into consideration the planned interim analyses, the study is powered to assure 80% likelihood of identifying a difference in success rates greater than or equal to 7%. Sample size estimation is based on the comparison of independent proportions. This estimation approach is conservative as the proposed regression analysis is generally more powerful than chi square test on individual outcomes. The maximum sample size required for randomization is 1314 subjects (657/treatment group). Although every attempt will be made to avoid drop outs and losses to follow up, the required sample size is inflated for a 3% non-adherence rate. The 3% rate is consistent with pilot data and the ALIAS study rates. The estimated total of subjects required is a maximum of 1400. The analysis plan does include a sample size re-estimation so this number could potentially change. Details of the re-estimation are in the Statistical Analysis Plan (SAP).

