6. RANDOMIZATION

A web-based central randomization system will be developed by the SDMC and installed on the WebDCU™ SHINE study website using a combination of covariate balance and response-adaptive randomization (RAR) method.⁶ The randomization design is aimed to preserve the randomness of treatment assignment, prevent serious imbalance in important baseline prognostic variables and promote subject recruitment while preserving the statistical test power. In summary, the probability of treatment assignment under the proposed scheme will be based on the prevention of serious imbalance in the pre-specified prognostic variables and the favorable outcome rate of each treatment arm. The specific prognostic variables at the time of randomization are: baseline NIHSS strata (3-7; 8-14; 15-22); use of IV thrombolysis (Y/N); and, site. Favorable outcome will be based on the baseline severity adjusted dichotomized mRS as previously described.

The SHINE Randomization algorithm will be fully detailed and documented in the SHINE Randomization Plan and Validation Documents. These documents will be developed prior to the enrollment initiation and stored in a secure location at the SDMC. The documents will be archived with the study database at the end of the trial. In summary, the trial will start with a 1:1

allocation scheme focusing on covariate balance. The RAR will be implemented once an adequate amount of primary outcome information is collected. With RAR, each enrolling subject will have a higher probability (greater than 50% chance) of being assigned to the treatment arm with the higher success rate based on previous subjects' responses. The SDMC's computer system will run both the 1:1 allocation and the RAR. Participating sites and members of the study team will not notice any difference between the randomization schemes and sites will only need to press one randomization button on the computer screen to obtain the assigned treatment during the course of the study. To ensure proper randomization, the unblinded statistical programmer will have access to the randomization information in order to oversee the quality control of the computer program.

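### Minor, free improvement: SAP 10.2 tests favorable 90-day NIHSS and Barthel unadjusted, although baseline NIHSS stratum is a randomization factor and a primary-model covariate

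*SAP*

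**What the plan says.** SAP 10.2 defines a favorable outcome as 0 or 1 on the 90-day NIHSS and 95-100 on the Barthel Index. It then states: "Each of these dichotomous outcomes will be analyzed using a chi-square test at a significance level of 0.05". It claims 80% power at 1400 patients for a 7-point NIHSS difference (control 25%) and an 8-point Barthel difference (control 40%).

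Elsewhere the plan treats baseline severity as prognostic:

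- SAP 6 randomizes on "baseline NIHSS strata (3-7; 8-14; 15-22); use of IV thrombolysis (Y/N); and, site", with the stated aim to "prevent serious imbalance in important baseline prognostic variables".
- SAP 10.1.2 fits the primary model with "baseline NIHSS strata (3-7, 8-14, 15-22) and thrombolysis use (Yes/No; includes both IV and IA therapies) as covariates".
- SAP 11.2 adjusts the Cox model for death for baseline NIHSS score.
- Protocol 12.1 says of the primary analysis that "the proposed regression analysis is generally more powerful than chi square test on individual outcomes".

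SAP 10.2 also plans adjusted analyses of the secondary outcomes, as further analyses after the main tests. Their covariates are those "listed above in the primary analysis section as well as additional covariates identified at the time of analysis". The sentence in 10.1.2 that lists named covariates reads: "Specific covariates include age, gender, race, ethnicity, admission blood glucose, previous stroke, lacunar subtype, and time between stroke onset and treatment". Baseline NIHSS and thrombolysis are not in that list, although both are in the primary model described in the same section.

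**The concern.** The primary endpoint moves its mRS cutpoint with baseline severity, and the plan still adjusts for stratum. The NIHSS and Barthel endpoints do not move: a patient entering at NIHSS 4 and one entering at NIHSS 20 must reach the same score. If the chance of reaching it falls with baseline severity, much of the outcome variance lies between strata. The chi-square test counts that variance as noise, and a stratified test removes it.

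There is a second consequence. When randomization balances the strata, the chi-square standard error is larger than the true sampling variation, so the test rejects less often than 5% under the null.

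At stake is some power on two secondary outcomes, together with a small gap in pre-specification: the reader cannot tell whether the planned adjusted analyses contain the stratum.

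**Working it through.** **Inputs from the SAP.** 10.2: 1400 patients, alpha 0.05, NIHSS 25% vs 32%, Barthel 40% vs 48%. **Assumed:** two-sided tests (10.2 does not say), 700 per arm, severity mix 45/35/20% over NIHSS 3-7, 8-14 and 15-22, control rates by stratum as tabulated below, and a common odds ratio.

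**1. The plan's own figure.** Power = Φ[(d − 1.96·SE0)/SE1], where SE0 = √(2p̄(1−p̄)/n) and SE1 = √((p₁(1−p₁)+p₂(1−p₂))/n).

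- NIHSS: SE0 = √(2×0.285×0.715/700) = 0.02413; SE1 = √((0.1875+0.2176)/700) = 0.02406; (0.07 − 0.04729)/0.02406 = 0.944; power 82.7%.
- Barthel: SE0 = √(2×0.44×0.56/700) = 0.02653; SE1 = √((0.24+0.2496)/700) = 0.02645; (0.08 − 0.05200)/0.02645 = 1.059; power 85.5%.

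At 657 per arm these are 80.3% and 83.3%. The stated 80% is met.

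**2. Worked case: NIHSS, moderate gradient.** Control rates are 0.401/0.170/0.050. An odds ratio of 1.481 gives 0.498/0.233/0.073, which averages 32%. The mid-rates are 0.449/0.202/0.061.

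- Within-stratum variance: 0.45×0.449×0.551 + 0.35×0.202×0.798 + 0.20×0.061×0.939 = 0.179, against 0.285×0.715 = 0.204 unstratified.
- Stratified SE0 = √(2×0.1792/700) = 0.02263. True SE1 with balanced strata = 0.02254.
- Stratified test: (0.07 − 1.96×0.02263)/0.02254 = 1.138; power 87.2%.
- Chi-square with balanced strata: (0.07 − 1.96×0.02413)/0.02254 = 1.007; power 84.3%.
- Gain: 2.9 points.

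**3. All gradients, strata exactly balanced (same formulas).**

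| Outcome, gradient | Control rates by stratum | Chi-square | Stratified | Gain (points) |
|---|---|---|---|---|
| NIHSS, shallow | 0.32/0.22/0.14 | 83.1% | 83.8% | 0.7 |
| NIHSS, moderate | 0.40/0.17/0.05 | 84.3% | 87.2% | 2.9 |
| NIHSS, steep | 0.47/0.10/0.02 | 86.1% | 91.5% | 5.4 |
| Barthel, shallow | 0.50/0.37/0.23 | 86.1% | 87.1% | 1.0 |
| Barthel, moderate | 0.60/0.30/0.12 | 87.6% | 90.9% | 3.3 |
| Barthel, steep | 0.71/0.21/0.05 | 90.5% | 96.1% | 5.7 |

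Gains are taken from unrounded powers. Simulation (100,000 trials each, Pearson chi-square against Cochran-Mantel-Haenszel) gives 0.8, 2.8 and 5.4 points for NIHSS and 1.1, 3.4 and 5.8 for Barthel. With no gradient the gain is 0.

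**4. Looser balance (simulated gain, NIHSS / Barthel).**

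- Half the imbalance of simple randomization: 0.9/1.0 (shallow), 3.1/4.0 (moderate), 6.4/7.2 (steep).
- No balancing: 1.1/1.7, 4.6/5.5, 8.4/10.6. SAP 6 does balance, so these are upper figures.

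**5. Type I error, moderate gradient.** For NIHSS under the null with exact balance, the within-stratum variance is 0.45×0.401×0.599 + 0.35×0.170×0.830 + 0.20×0.050×0.950 = 0.167, against 0.25×0.75 = 0.1875. The effective critical value is 1.96/√(0.167/0.1875) = 2.08, so the size is about 0.038. The same step gives 0.033 for Barthel. With partial balance, simulation gives about 0.042 and 0.038; with none, about 0.05. The stratified test stays at 0.049-0.052.

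**6. Form of the model.** A check with 6,000 trials used the moderate gradient, exact balance and an assumed 40% thrombolysis use with no effect. Chi-square, Mantel-Haenszel, logistic Wald and log-link relative-risk Wald gave 84.2/87.1/87.1/87.1% for NIHSS and 88.2/91.4/91.5/91.4% for Barthel. The gain comes from the stratum and not from the choice of model, and the thrombolysis term costs nothing.

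**7. A different mix.** With 50/30/20% and weak, moderate or strong gradients, relative efficiency is about 1.03 to 1.39.

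**The case against.** The strongest reply is that adjustment is already planned. SAP 10.2 promises adjusted analyses of all secondary outcomes, and the primary section it points to does name NIHSS strata as covariates. On that reading, all that remains is which analysis is labelled the main one. This stands in part: a reader should not infer that the plan leaves the secondary outcomes unadjusted. But the adjusted analyses are follow-ups, the list of named covariates omits the stratum, and some covariates are left to the time of analysis. Inclusion is possible but not assured.

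The size is also open to challenge. No document gives a severity mix or stratum rates. SAP 6 plans response-adaptive allocation, and SAP 10.1.3 gives a 0.66 probability of stopping before the final look under the alternative. Neither was modelled. This stands: the direction is secure, the size is not.

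Stronger readings that the documents do not support:

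- *The secondary tests are invalid or underpowered.* They are not. The chi-square exceeds 80% power in every case above and errs on the conservative side.
- *Protocol 12.1 contradicts SAP 10.2.* Its remark concerns the primary sample size. It supports the suggestion by analogy only.
- *The thrombolysis term should be changed.* SAP 10.1.2 says it compares groups "after controlling for the variables included in the randomization scheme", yet its term covers IV and IA therapy while SAP 6 randomizes on IV only, and site is left to SAP 9. No numerical effect was shown, and the IV-or-IA term is an explicit choice. The imputation model in SAP 8 takes its variables from the primary analysis and so inherits that definition. At most this calls for a clarification of wording.
- *SSQOL loses power in the same way.* This was not computed.

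**Conclusion.** The point holds as a minor efficiency improvement. Baseline NIHSS stratum is already recorded, balanced and used in the primary model, and the main tests of two fixed-cutpoint secondary outcomes leave it out. Under the stated assumptions (45/35/20% mix, 1400 patients, 50:50 allocation, balanced strata, common odds ratio) the cost is 0 points of power with no gradient, about 1 with a shallow one, about 3 with a moderate one and about 5.5 with a steep one, and somewhat more if balance is looser. To match the stratified test under exact balance, the chi-square would need about 1450, 1550-1575 or 1675-1750 patients for the three gradients. With full or partial balance and a moderate gradient, the chi-square runs at a type I error of about 0.033-0.042, while the stratified test stays near 0.05. In no scenario examined did stratifying lose power.

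**What to change.** In SAP 10.2, before unblinding:

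1. Make the main test of favorable 90-day NIHSS and of favorable Barthel the primary model's form: PROC GENMOD with treatment, baseline NIHSS stratum and thrombolysis use as defined in 10.1.2, a Wald test, and the adjusted relative risk with its 95% confidence interval.
2. Keep the chi-square test and the absolute risk difference as supportive results, so that the scale of the 10.2 power statement is still reported.
3. State that every adjusted model for a secondary outcome includes baseline NIHSS stratum.

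The thrombolysis definition in the primary, imputation and Cox models need not change, and nothing is proposed for SSQOL. If 10.1.2 is being edited anyway, its sentence on the randomization variables could note that the thrombolysis term is broader than the randomization factor and that site is handled in SAP 9.

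The cost is SAP wording only. The stratum is recorded for randomization and thrombolysis use is already needed for the primary model, so no patients, visits or data are added.
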